### **3.2 Secondary Objectives:**

- Evaluate IPSS and QoL after discontinuation of indwelling bladder catheter (IBC) post PAE
- Evaluation of device-related adverse events
- Evaluation of procedure-related adverse events
- Evaluate frequency of indwelling bladder catheter (IBC) removal post PAE
- Technical Success
  - Successful embolization of treated prostate gland
- Evaluation of additional treatments for refractory or recurrent LUTS due to BPH post PAE
- Evaluation of change from baseline in erectile function at 12 months post PAE using the Sexual Health Inventory for Men (SHIM). 12-16

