## 6 Visit schedule and actions

### 6.1 Baseline Visit

The following baseline data will be collected:

- Date patient signs informed consent
- Demographics
- Prior BPH procedures
- Current Medication for BPH (5 $\alpha$ -Reductase inhibitors,  $\alpha$ -blockers, ED medications, OTC medications, etc.)

The following baseline data will be collected within 4 weeks of the study PAE procedure:

- International Prostate Symptom Score (IPSS)
  - Must be self-administered by patient
- Sexual Health Inventory for Men (SHIM)
  - Must be self-administered by patient

The following baseline data will be collected within a timeframe consistent with standard of care:

- Prostate Size Assessment
- Urinary Evaluations (Indwelling urinary catheter use, Maximum urine flow rate (Qmax), and Post void residual volume (PVR)), if done
- Prostate specific antigen (PSA), if done

The following baseline data will be collected within 12 months of the study PAE procedure:

- Prostate Biopsy, if done

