## **6.2 Prostatic Artery Embolization (PAE) Procedure Information**

The following procedural data will be collected:

- Date of procedure
- Date and time of discharge
- Embolization start and end time
- Access site (Femoral/Radial)
- Was the PErFecTED technique used? (If yes, prostate lobe(s) used on)
- Was Foley catheter with contrast used?
- Lobes embolized (Right/Left/Both)
- Size of Embosphere Microspheres
- Total Volume Administered
- Device or Procedure-related adverse events

Patients will be given a form on which to record Device or Procedure-related adverse events during the first month post procedure.

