## **6.4 Visit 2, 3 & 4: 3 Months ( $\pm 2$ weeks), 12 Months ( $\pm 8$ weeks), 24 Months ( $\pm 8$ weeks) Follow-Up**

Study participation will last for a total of 24 months ( $\pm 8$  weeks). Traditional visit windows are being expanded to allow for potential impacts due to COVID-19.

The following information will be collected:

- International Prostate Symptom Score (IPSS)
  - Must be self-administered by patient
- Device or Procedure-related adverse events
- Changes in indwelling urinary catheter use
- BPH related medications
- Additional prostate procedures and/or imaging

- Urinary Evaluations (Qmax and PVR), if done
- Sexual Health Inventory for Men (SHIM), 12-months only
  - Must be self-administered by patient
- Prostate specific antigen (PSA), if done

If approved by the IRB/EC, patients may receive an honorarium for complying with follow-up data collection at 12 and 24 months.

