#### **8.1.2 Secondary Endpoints**

The following are the secondary endpoints:

- IPSS measured at 3, 12, and 24 months post-baseline
- Device or Procedure-Related Adverse event rate at post-procedure, 3, 12, and 24 months
- Technical Success defined as the successful embolization of the treated prostate gland
- Frequency of indwelling bladder catheter removal post PAE at 3, 12, and 24 months
- Number of patients and types of treatment for refractory or recurrent LUTS due to BPH post PAE at 3, 12, and 24 months
- Change from baseline in Sexual Health Inventory for Men (SHIM) at 12 months post-PAE.

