### 8.4.2 Evaluable Analysis Set (EAS)

Includes FAS patients where there are no significant deviations (e.g. not meeting the inclusion/exclusion criteria) from the protocol that did not have an indwelling catheter at the end of the procedure.

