### **8.5.3.7 Removal of In-dwelling catheter**

Using the FAS, for patients who had an indwelling catheter during the procedure, the proportion of indwelling bladder catheter (IBC) removal post-PAE will be reported at 3 and 12 months PAE.

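### Catheter removal is declared as a secondary endpoint at 3, 12 and 24 months, but its analysis stops at month 12 and its denominator does not exclude catheters placed only for the procedure

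*Combined protocol and SAP*

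**What the plan says.** **Time points.** The secondary objective in section 3.2 sets no time limit: "Evaluate frequency of indwelling bladder catheter (IBC) removal post PAE". Section 8.1.2 turns it into an endpoint at three visits: "Frequency of indwelling bladder catheter removal post PAE at 3, 12, and 24 months". Section 8.5.3.7, the only section that analyses it, says the proportion "will be reported at 3 and 12 months PAE" and gives no reason for leaving out month 24.

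**Denominator.** Section 8.5.3.7 uses the FAS and computes the proportion "for patients who had an indwelling catheter during the procedure".

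**Catheter data collected.**
- Baseline (section 6.1): "Urinary Evaluations (Indwelling urinary catheter use, Maximum urine flow rate (Qmax), and Post void residual volume (PVR)), if done".
- Procedure (section 6.2), as a separate item: "Was Foley catheter with contrast used".
- Months 3, 12 and 24 (section 6.4): "Changes in indwelling urinary catheter use". Table 1 agrees for these three visits.

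**Another reference point.** The Evaluable Analysis Set in section 8.4.2 is limited to men who "did not have an indwelling catheter at the end of the procedure".

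**The concern.** There are two separate problems in one sentence of the analysis plan.

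First, the endpoint list and the analysis section disagree on the time points. An analyst who follows 8.5.3.7 produces no 24-month result for a declared endpoint, in a study whose stated purpose (section 2) is long-term evaluation. If the result is added once the data have been seen, it will look like a post hoc choice.

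Second, the denominator is fixed by catheter status during PAE, while the question of interest is whether men who came to PAE with a catheter become free of it. The plan itself foresees that a Foley may be used in the procedure, and nothing in 8.5.3.7 says that such a catheter does not count. Two analysts could therefore obtain different removal rates from the same data. The study has a single arm, so no comparator would expose an inflated rate.

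**Working it through.** The documents state no expected removal rate, subgroup size or precision for this endpoint, so there is no figure to reproduce. The check is a comparison of the text followed by an illustration.

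**1. Month 24**

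| Source | Months |
|---|---|
| Endpoint, 8.1.2 | 3, 12, 24 |
| Data collection, 6.4 and Table 1 | 3, 12, 24 |
| Study reporting, 8.5.6 | after the primary endpoint (12 months), then at 24 |
| Analysis of additional treatments, 8.5.3.5 | 3, 12, 24 |
| Analysis of catheter removal, 8.5.3.7 | 3, 12 |

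Only the catheter analysis drops month 24. The comparable analysis of additional treatments keeps it.

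**2. Who is in the denominator**

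| Man | Catheter at baseline (6.1) | In 8.5.3.7 as worded | In EAS if otherwise eligible (8.4.2) |
|---|---|---|---|
| Catheter before PAE, still in at the end | yes | yes | no |
| Foley for PAE only, out before the end | no | yes, read literally | yes |
| Foley for PAE only, still in at the end | no | yes, read literally | no |

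The plan uses three reference points for catheter status: baseline, during the procedure and end of procedure. The second and third rows show where the literal wording admits men who had no catheter beforehand.

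**3. How far the rate could move (illustration only)**

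Inputs:
- C, men with a catheter before PAE. The earlier cohort in section 1 had 54/286 = 18.9%. Applied to the maximum enrolment of 500, this is 500 × 54/286 = 94.4, taken as 94, leaving 406 others.
- p, true removal rate in those men. Not in the documents; 50%, 70% and 85% are assumed.
- f, share of the other 406 with a procedural Foley that is counted. Not in the documents; 10%, 25%, 50% and 100% are assumed, giving m = 41, 102, 203 and 406.
- All procedure-only catheters are assumed removed by month 3 and counted as removals.

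Formula: reported rate = (pC + m)/(C + m). In whole men, pC is 47, 66 or 80.

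Example with p = 70% and f = 10%: (66 + 41)/(94 + 41) = 107/135 = 79.3%, against 66/94 = 70.2%.

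| Assumed p | f = 0 (exact 95% CI) | 10% | 25% | 50% | 100% |
|---|---|---|---|---|---|
| 50% | 50.0% (39.5 to 60.5) | 65.2% | 76.0% | 84.2% | 90.6% |
| 70% | 70.2% (59.9 to 79.2) | 79.3% | 85.7% | 90.6% | 94.4% |
| 85% | 85.1% (76.3 to 91.6) | 89.6% | 92.9% | 95.3% | 97.2% |

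The shift equals (1 − p) × m/(C + m). At f = 10% it is 0.298 × 41/135 = 9.1 points for p = 70%, and 0.149 × 41/135 = 4.5 points for p = 85%. If procedure-only catheters are removed at a rate q below 100%, the shift becomes (q − p) × m/(C + m), which is upward whenever q exceeds p.

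**The case against.** The time-point mismatch is hard to defend, but its consequence can be overstated. A reader might infer that the long-term result is lost. The documents do not support that: section 8.1.2 still declares the 24-month endpoint, section 6.4 and Table 1 collect the data, and section 8.5.6 provides for a report at 24 months. What is missing is the planned analysis.

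The denominator has a reasonable defence. Section 8.5.3.7 speaks of an indwelling catheter and, in the same sentence, of an indwelling bladder catheter. Sections 3.2 and 4 use that term for a continuing state, one in which the IPSS may not be relevant. The Foley with contrast in section 6.2 is a separate yes/no item and is not called indwelling. On that reading, the denominator is simply men who arrived with a catheter in place. This stands as a plausible intention, but the text does not state it.

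A reader might also infer that every man catheterised for the procedure counts, that his catheter comes out routinely, and that the rate is therefore certainly inflated. The documents do not say when a procedural Foley is removed. If it came out before the procedure ended, it is unclear whether that would count as removal after PAE. Inflation needs both the broad denominator and those removals being counted.

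Finally, the removal rates and Foley shares in the illustration have no source in the documents, and the 18.9% share comes from a different cohort. That objection stands in full.

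**Conclusion.** The concern holds, with different certainty for its two parts.

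The month-24 omission is a plain contradiction between 8.1.2 and 8.5.3.7. It rests on no assumption.

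The denominator is an ambiguity that carries a risk of upward bias; the bias is not established. The literal wording does not exclude procedure-only catheters. On the assumptions shown, the reported rate could be 79% to 94% where the true rate is about 70%, but only about 4.5 points too high at 85% true removal and 10% procedural use. If the sponsor meant pre-existing catheters only and the analysis is run that way, this shift is zero. These figures show sensitivity to the definition and do not estimate a bias in this trial.

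The primary endpoint is not affected. The change should be made, but the study does not depend on it.

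**What to change.** Amend section 8.5.3.7 in two places:
1. Report the removal proportion at 3, 12 and 24 months, each with the exact 95% confidence interval already named in section 8.5.1.7.
2. Define the denominator as FAS patients with an indwelling bladder catheter already in place before PAE, and state that catheters placed only for the procedure are excluded.

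Defining the group by status before PAE avoids missing a man catheterised between the baseline visit and the procedure. It should not be narrowed by the reason for the catheter, because no section lists that reason as collected.

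The cost is small. The 24-month data are already scheduled. However, baseline catheter use sits among urinary evaluations collected only where done, and section 6.2 lists no item on whether a catheter was already in place. The sponsor must therefore confirm that status before PAE is recorded for every patient. The denominator may also be smaller and the interval wider: in the illustration, 94 men at about 70% give 59.9% to 79.2%.

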### 8.5.4 Safety Analyses

All device or procedure related adverse events (AEs) collected will be summarized cumulatively throughout the follow-up time. The frequency count of AEs and the unique number of subjects who had the AEs will be presented. Also, the frequency and percentage of patients who had a Serious AE (SAE), or a treatment-related serious AE will be tabulated separately. If a patient experienced multiple AEs, only the most severe event or the most intense relationship to the study device would be counted within an AE code. The following information will be reported about each AE; start date, stop date, severity, relationship, expectedness, outcome, and duration.

The time-sensitive nature of any response variable may be displayed by using a Kaplan-Meier plot.

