## 9 Device or Procedure-Related Adverse Events

A Device or Procedure-related adverse event is defined in this post market study as any event that began on or after the date of the PAE procedure and is considered related to the study procedure and/or device by the investigator. All related events must be reported in the case report form and followed until resolution.

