### 9.2 Relationship of Adverse Event to Device and/or Procedure

The Investigator, based on his/her clinical judgment and the following definitions, must determine the relationship of the adverse event to the device and/or procedure:

- Possible: The AE/SAE follows a reasonable temporal sequence from the time of study procedure, and/or follows a known response pattern to the study procedure but could have been produced by other factors.
- Probable: The AE/SAE follows a reasonable temporal sequence from the time of study procedure, follows a known response pattern to the study procedure, and cannot reasonably have been produced by other factors.
- Definite: The AE/SAE follows a reasonable temporal sequence from the time of study procedure; follows a known response pattern to the study procedure; and cannot have been produced by other factors.

[figure not shown]

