### 9.3 Device or Procedure-Related Serious Adverse Events

A device or procedure-related serious adverse event is defined in this post market study as any event that began on or after the date of the PAE procedure and is considered related to the study procedure and/or device by the investigator. A device or procedure-related adverse event will be considered serious if it meets one of the following criteria:

- Results in death
- Is life-threatening. Life-threatening means that the patient was at immediate risk of death from the reaction as it occurred, i.e., it does not include a reaction which hypothetically might have caused death had it occurred in a more severe form
- Requires in-patient hospitalization or prolongation of existing hospitalization. Hospitalization admissions and/or surgical operations scheduled to occur during the study period, but planned prior to study entry are not considered AEs if the illness or disease existed before the patient was enrolled in the trial, provided that it did not deteriorate in an unexpected manner during the trial (e.g., surgery performed earlier than planned)
- Results in persistent or significant disability/incapacity. Disability is defined as a substantial disruption of a person's ability to conduct normal life functions
- Is a congenital anomaly/birth defect
- Is an important medical event. An important medical event is an event that may not result in death, be life-threatening, or require hospitalization, but may be considered an SAE when, based upon appropriate medical judgment, it may jeopardize the patient or patient and may require medical or surgical intervention to prevent one of the outcomes listed in the definitions

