#### 9.4 Reporting of Serious Adverse Events

Any treatment-related SAE that occurs on or after the date of the PAE or worsened in severity or frequency after the PAE must be reported to the Sponsor immediately (not to exceed 24 hours within site notification of the event) in the case report form or via email. It is the responsibility of Investigators to inform their IRB/EC of complications or serious injury as required by their IRB/EC procedure and/or federal law. Merit Medical is responsible for relaying information about serious adverse events and/or treatment related adverse events to the other participating Investigators and regulatory bodies as required.

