## 18 Safety Medical Monitor

An independent safety medical monitor shall be responsible for systemic review and adjudication of specified events (e.g., all treatment-related adverse events and all deaths) . At a minimum, assess the reported event with the associated documented risks of device, vascular embolization, and PAE treatment.

Potential risk for Embosphere Microspheres:

- Immune reaction in patients who are hypersensitive to collagen or gelatin (careful consideration should be given prior to using this product in patients who are suspected to be allergic to injections containing gelatin stabilizers)

Potential risk for vascular embolization:

- Paralysis resulting from untargeted embolization or ischemic injury from adjacent tissue edema
- Undesirable reflux or passage of Embosphere Microspheres into normal arteries adjacent to the targeted lesion or through the lesion into other arteries or arterial beds, such as the internal carotid artery, pulmonary, or coronary circulations
- Pulmonary embolism
- Ischemia at an undesirable location, including ischemic stroke, ischemic infarction (including myocardial infarction), and tissue necrosis
- Capillary bed occlusion and tissue damage
- Vessel or lesion rupture and hemorrhage
- Vasospasm
- Recanalization
- Foreign body reactions necessitating medical intervention
- Infection
- Complications related to catheterization (e.g., hematoma at the site of entry, clot formation at the tip of the catheter and subsequent dislodgment, and nerve and/or circulatory injuries, which may result in leg injury)
- Allergic reaction to medications (e.g., analgesics)
- Allergic reaction o contrast media or embolic material
- Pain and/or rash, possibly delayed form the time of embolization
- Death
- Blindness, hearing loss, loss of smell, and/or paralysis

PAE specific potential complications:

- Non-targeted embolization of the rectum, bladder, scrotum, penis, or other areas
- The most frequent post-procedure complication includes “Post-PAE Syndrome,” which includes nausea, vomiting, fever, pelvic pain, burning sensation, dysuria, and frequent or urgent urination
- Skin burn (radiation exposure) from prolonged fluoroscopy time
- Blood in urine, semen, or stool
- Bladder spasm
- Hematoma at the catheter site
- Urinary tract infection
- Urinary retention
- Constipation

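### The separate SAE count in Section 8.5.4 duplicates the treatment-related SAE count, because only related events are captured, and deaths judged unrelated have no stated route to the safety monitor

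*Combined protocol and SAP*

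**What the plan says.** The safety analysis in Section 8.5.4 opens with its scope: "All device or procedure related adverse events (AEs) collected will be summarized cumulatively throughout the follow-up time". It then adds that "the frequency and percentage of patients who had a Serious AE (SAE), or a treatment-related serious AE will be tabulated separately".

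The sections that supply the data are narrower than that second sentence suggests:

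- Section 9 limits adverse events to those that began on or after the procedure date and that the investigator judges related ("is considered related to the study procedure and/or device by the investigator"). The recording duty is "All related events must be reported in the case report form and followed until resolution".
- Section 9.3 makes seriousness a property of related events only: "A device or procedure-related adverse event will be considered serious if it meets one of the following criteria".
- Section 9.4 sets the expedited reporting duty for "Any treatment-related SAE that occurs on or after the date of the PAE", or that worsened after it.
- Sections 6.2 to 6.4 and Table 1 collect device or procedure-related events at the procedure and at each visit. The patient's form for the first month has the same limit.

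Section 18 gives an independent safety medical monitor the review and adjudication of specified events, with "all treatment-related adverse events and all deaths" as the example. Its method is left to a safety monitoring charter.

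**The concern.** Two rows that are tabulated separately should be able to differ. Here they cannot. A reader who sees an SAE row beside a treatment-related SAE row will naturally take the first as SAEs of any cause, and if the two agree, may conclude that every SAE in the cohort was treatment-related or that hardly any other SAEs occurred. The data support neither conclusion.

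The second issue is what the monitor can do. This is an open-label, single-arm study with long-term safety as a stated goal, and the device or procedure-related event rate is a secondary endpoint. Independent adjudication is the main check on the investigator's attribution. For non-fatal events, that attribution also decides what enters the database. For deaths, the plan gives the monitor a wider remit than its reporting rules are written to serve.

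**Working it through.** The plan states no SAE rate or safety precision target, so there is no figure to reproduce. The check traces the events from definition to table.

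**Step 1: the two SAE counts.** Let R be the events that the investigator considers related and S the events that meet a seriousness criterion.

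- Events entering the case report form (Sections 6, 9): R.
- Events that can be called an SAE (Section 9.3): R ∩ S.
- Events reported as SAEs (Section 9.4): R ∩ S.
- SAE row in Section 8.5.4: patients with an event in R ∩ S.
- Treatment-related SAE row: patients with an event in R ∩ S.

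The rows are the same set, so the overlap is 100%. *Treatment-related* does not appear to be a narrower class: Section 8.5.3.2 uses it for the endpoint titled device or procedure-related. The rows could differ if the second used the monitor's adjudicated relatedness, but neither Section 8.5.4 nor Section 18 says so. Section 8.5.3.2 refers the rate analysis to Section 9.3, which contains definitions only and does not settle the matter.

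**Step 2: adjudication of non-fatal events.** Under Section 9.2 the investigator "must determine the relationship of the adverse event to the device and/or procedure". The levels in the text are possible, probable and definite; a figure at that place was not available for this review. A non-fatal event judged unrelated is outside R and has no described route to the monitor. The adjudicated related set is therefore a subset of R: its count can stay the same or fall, but not rise.

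**Step 3: what that could mean in numbers (illustration only).** N = 500 is the enrolment ceiling in Section 4. The rest are assumptions: A, the share of patients with an SAE of any cause; s, the share with an investigator-related SAE; u, the share of the remainder that an adjudicator would call related. Nothing is adjudicated down, and all SAEs are treated as non-fatal.

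- Current capture: adjudicated related rate = s.
- Full capture: adjudicated related rate = s + (A − s) × u.

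With A = 10–30% and s = 2–5%, both SAE rows would show 500 × 0.02 = 10 to 500 × 0.05 = 25 patients, against 500 × 0.10 = 50 to 500 × 0.30 = 150 with an SAE of any cause. For the related rate under full capture:

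- s = 2%, u = 5%: 2% + 8% × 0.05 = 2.4% (A = 10%) to 2% + 28% × 0.05 = 3.4% (A = 30%).
- s = 2%, u = 20%: 2% + 8% × 0.20 = 3.6% to 2% + 28% × 0.20 = 7.6%.
- s = 5%: from 5% + 5% × 0.05 = 5.25% (A = 10%, u = 5%) to 5% + 25% × 0.20 = 10.0% (A = 30%, u = 20%).
- u = 0: no difference.

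The range runs from nothing to a large difference, and the documents do not say where in it the study would fall.

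**Step 4: deaths.** Section 18 lists all deaths, without a relatedness condition. Section 9.4 requires reporting of treatment-related SAEs only. Between the two:

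- Section 7 puts the reason for withdrawal or discontinuation on the end of study form.
- Section 8.5.1.2 uses the date of death in the last-contact derivation.
- Section 8.5.1.6 has a rule for partial dates of death.

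Some unrelated deaths will therefore be known. No section requires their cause or says that they go to the monitor. Section 7 also ends data collection after a disqualifying BPH procedure, so later deaths need not be recorded.

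**The case against.** The strongest defence is that related-only collection is deliberate and consistent. The safety objectives in Section 3.2 are device-related and procedure-related events, the device already has the indication, and there is no comparator arm in which attribution could differ. The threshold for *possible* in Section 9.2 is low, which limits under-attribution. Catheter changes, further prostate procedures and BPH medication are collected whatever their cause, and monitors review source documents (Section 17). All of this stands as a defence of the design. It does not make the duplicate row meaningful.

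Three stronger readings are tempting and should be resisted.

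- A reader might infer that Section 8.5.4 promises an all-cause SAE table. It does not: it never says all SAEs, and its opening sentence limits the summary to related events. The defect is a redundant row that invites misreading.
- A reader might infer that the monitor never sees an event judged unrelated and can only move events down. Section 18 includes all deaths, so an unrelated death could reach the monitor and be reclassified as related. The monitor could also raise seriousness, severity or the grade of relationship. The one-way limit concerns only the related/unrelated decision for non-fatal events.
- A reader might infer that the related-SAE rate is understated by some definite share, or that independent adjudication is defeated. No figure in the documents supports either.

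The charter may widen what the monitor receives, but it cannot supply events that were never recorded.

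**Conclusion.** The point holds in limited form. The two SAE counts coincide entirely, given the definitions in Sections 9 to 9.4 and on the reading that both rows use investigator-assessed relatedness. No all-cause SAE percentage can be obtained from the planned data. The intended adjudication of all deaths lacks a matching duty to report unrelated deaths with their cause, although some will be known. For non-fatal events, relatedness can be confirmed or removed on adjudication but not added.

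The size of any effect on the related-SAE rate is unknown. It is zero if investigators classify every related event as related, but the study as planned could not show that. Correcting the row and the death reporting is a needed repair; full all-cause SAE capture is a larger design choice, not the correction of an error.

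**What to change.** **Minimum change.**

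- In Sections 9 and 9.4, require every death, with its cause and regardless of relatedness, to be recorded and sent to the existing monitor.
- In Section 8.5.4, replace the two SAE counts with one table titled *device or procedure-related SAEs*, showing investigator-assessed and monitor-adjudicated relatedness side by side.
- State in the same place that all-cause SAE rates are not available from this study.

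The cost is a cause-of-death entry for each death and edits to the text and table shells.

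**If the sponsor wants to keep a separate SAE row.** Record all SAEs regardless of relatedness, add a *not related* level to Section 9.2 if none exists, and send these events to the monitor. Non-serious events can stay limited to related ones. The downside is real: more SAE forms and 24-hour reports over 24 months in up to 500 men, with the matching form changes and more work for the monitor. Under the assumed shares above, that means SAE data for 50 to 150 patients instead of 10 to 25.
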